#### **4.3 RESIDUAL RISKS ASSOCIATED WITH THE INVESTIGATIONAL DEVICE, AS IDENTIFIED IN THE RISK ANALYSIS REPORT**

The details of the residual risks identified in the different risk analysis (e.g., failure mode and effects analysis) are described in the RPDS IB Section 6.

#### **4.4 RISKS ASSOCIATED WITH PARTICIPATION IN THE CLINICAL INVESTIGATION**

The benefit and risks associated with participation in this study are outlined in the Informed Consent Form (ICF) and will be explained to the patient by the investigator. Ranibizumab has a well characterized safety profile, with clearly identified and potential risks associated with its use, which is described in the RPDS IB. The safety and tolerability of ranibizumab exposure delivered through the Implant were investigated in a Phase I prospective, open-label study in a wet AMD patient population by FSV4 at a single site in Latvia. The surgical procedure associated with Implant insertion could

## **Appendix 21**

### **Ranibizumab Port Delivery System: Device Clinical Investigation Plan (cont.)**

potentially lead to ocular AEs. These include, but are not limited to: ocular tissues inflammation or infection, conjunctival erosion, damage to the sclera, endophthalmitis, hypotony, suprachoroidal hemorrhage, and retinal detachment. The RPDS IFU describes all of the procedures necessary for successful insertion, refilling, and explantation of the Implant. It is imperative that specific surgical procedures are adhered to in order to minimize the risk of ocular AEs related to the procedure.

#### **4.5 POSSIBLE INTERACTIONS WITH CONCOMITANT MEDICAL TREATMENTS**

At the discretion of their physician, patients may continue to receive all medications and standard treatments administered for other conditions with certain exceptions as detailed in the protocol Section 4.5.2.

#### **4.6 STEPS THAT WILL BE TAKEN TO CONTROL OR MITIGATE THE RISKS**

Patients not considered suited for receiving the RPDS in this clinical investigation are excluded as outlined under exclusion criteria (see the protocol Section 4.1.2).

Study investigators will be qualified ophthalmologists, trained in the management of retinal diseases and ocular surgery, and will be certified by a Sponsor-selected vendor to perform initial Implant fill, insertion, refill, and explantation. The surgical procedures involved in the use of the RPDS are also detailed in the RPDS IFU document.

Patients must adhere to the instructions for prohibited therapy (see Section 4.5) and dose interruptions/study treatment or study discontinuation criteria (protocol Table 6).

Prior to Implant insertion or explantation, patients will be required to verify that they have self-administered their antimicrobial eye drops to the study eye 4 times within the previous 24 hours. As per investigator's discretion, patients may also be required to have self-administered antimicrobial eye drops to the study eye 4 times within the 24 hours prior to Implant refills. It is required that all patients self-administer their antimicrobial drops again 4 times daily for 7 days following Implant insertion or explantation, and 4 times daily for 3 days following refills. Please see the protocol section 5.1 for additional details.

The insertion procedure and, if applicable, the explantation procedure must be performed in the surgery room while the refill procedure is permitted in the physician office setting.

The results of risk/benefit assessment from the overall risk analysis are described in the RPDS IB Section 6.

## **Appendix 21**

### **Ranibizumab Port Delivery System: Device Clinical Investigation Plan (cont.)**

#### **4.7 RISK-TO-BENEFIT RATIONALE**

The Phase I study provided preliminary evidence of a positive benefit–risk profile for the use of RPDS in patients with wet AMD and supports the evaluation of RPDS in a Phase II study. It is expected that in the Phase II study the drug efficacy of at least one Implant treatment arm will be similar to the control ITV monthly injection treatment arm.

Further details are included in the protocol Section 1.4.

#### **5. OBJECTIVES AND HYPOTHESES OF THE CLINICAL INVESTIGATION**

The objectives of the Phase II study are described in the protocol section 2. This RPDS CIP provides an overview of the device objectives and focuses on the parameters used for the assessment of RPDS functionality and safety.

##### **5.1 DEVICE OBJECTIVES**

- To evaluate the functionality of the Implant by assessing that there is no evidence of Implant clogging in more than 10% of patients in the Implant arms at Month 9
- To explore the serum ranibizumab concentration data with a PK model in an attempt to infer the concentration–time pattern in the vitreous humor and, if possible, derive information on the rate of ranibizumab release from the Implant
- To evaluate the safety of the RPDS, as measured by “Prespecified RPDS-associated AEs” (see protocol Section 6.5.1)

##### **5.2 HYPOTHESES, IMPLANT FUNCTIONALITY TO BE ACCEPTED OR REJECTED BY STATISTICAL DATA FROM THE CLINICAL INVESTIGATION**

The hypothesis to be established is that the initial Implant clogging rate does not exceed 10% of Implant arm patients at Month 9. In order to evaluate whether the Implant clogging rate exceeds 10% within the first 9 months, the proportion of clogged Implants will be estimated and the 90% confidence interval will be calculated. All clogging data from patients in the Implant arms will be pooled for this analysis.

In the study, the Implant will be judged as “failed” if it is determined that the RCE is clogged and can no longer deliver the ranibizumab into the ocular space (see [Table 6](#) “Failure to Operate State 1” and description below).

## Appendix 21 Ranibizumab Port Delivery System: Device Clinical Investigation Plan (cont.)

### 5.3 CLAIMS AND INTENDED PERFORMANCE OF THE IMPLANT THAT ARE TO BE VERIFIED

Intended performance of the Implant is demonstrated by successful operation of drug diffusing across the RCE in a manner consistent with Fick's Law of Diffusion as demonstrated in bench and animal studies. Implant functionality is demonstrated best in bench studies since there is no direct detectability in humans of Implant functionality that can be shown. No ethical method exists for directly measuring the flow of drug into the vitreous. Additionally serum pharmacokinetics is seen as too variable a measurement.

The clinical performance of the Implant will be demonstrated by measuring the rate of events related to the occurrence of Implant clogging.

The Implant will be assessed for possible clogging if the Implant is explanted. The following assessments will be performed:

- Serum pharmacokinetics of ranibizumab will be used to judge whether Implant clogging may have occurred. Aqueous and vitreous humor PK samples will also be collected at explantation and may be used to further assess possible Implant clogging. For each individual patient, possible Implant clogging will be documented if at least one of the following conditions is met:
    - For 40-mg/mL or 100-mg/mL dose groups: At Implant insertion and prior to the first refill: serum ranibizumab concentrations are below the lower limit of quantification (BLQ) or below the baseline serum ranibizumab concentration value at all time-points prior to refills, that is, on Day 1 (within 60 min of insertion – only if possible to collect), Day 2, Day 7, Day 14, and all monthly time points after insertion and prior to the first refill or to the last study visit for the patient, if no refill occurs
    - For the 10-mg/mL dose group: At Implant insertion and prior to the first refill: serum ranibizumab concentrations are below the lower limit of quantification (BLQ) value at all time-points prior to refills, that is, on Day 1 (within 60 min of insertion – only if possible to collect), Day 2, Day 7, Day 14, and all monthly timepoints after insertion and prior to the first refill or to the last study visit for the patient, if no refill occurs
- OR
- After the first refill: serum ranibizumab concentrations are BLQ or below the last pre-refill serum ranibizumab concentration value at all time-points post refills, that is, on Day 7, and all monthly time points prior to the next refill for two consecutive refills, or to the last study visit for the patient, if no further refill occurs

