### **5.1.1.5 Implant Clogging Assessment**

If an Implant is explanted, it will be analyzed for possible clogging using the following assessments:

- Serum pharmacokinetics of ranibizumab will be used to help judge whether Implant clogging may have occurred. Aqueous humor or vitreous PK samples will be collected at explantation and may be used to further assess possible Implant clogging. For each individual patient, possible Implant clogging will be documented if at least one of the following conditions are met:

At Implant insertion and prior to the first refill: serum ranibizumab concentrations are below the lower limit of quantification (BLQ) or below the baseline serum ranibizumab concentration value at all time-points prior to refills, that is, Day 1 (within 60 min of insertion), Day 2, Day 7, Day 14, and all monthly time points after Implant insertion and prior to the first refill or to the end of the study visit for this patient if no refill occurs.

After the first refill: serum ranibizumab concentrations are BLQ or below the last pre-refill serum ranibizumab concentration value at all time-points post refills, that is, Day 7, and all monthly time points prior to the next refill for 2 consecutive refills or to the end of the study visit for this patient if no further refill occurs.

- Implants identified that meet PK criteria for possible clogging will then undergo further diagnostics if explanted. The Implant “complete clogging” failure statistics will be summarized across all Implant patients based on the first 9 months of Implant insertion.

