## **Appendix 21**

### **Ranibizumab Port Delivery System: Device Clinical Investigation Plan (cont.)**

The Implants meeting PK criteria for possible clogging will then undergo further diagnostics if explanted to confirm whether treatment failure was due to clogging. The “implant complete clogging” failure statistics will be summarized across all patients based on the first 9 months of Implant insertion.

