### **7. STATISTICAL CONSIDERATIONS**

#### **7.1 STATISTICAL DESIGN, METHOD AND ANALYTICAL PROCEDURES**

One objective in the clinical study is to demonstrate that there is no evidence that the Implant clogging rate exceeds 10% of patients in the Implant arms at Month 9.

Implant clogging data from all patients that receive the Implant will be pooled together for this analysis. If there are 22 or fewer clogged Implants, among 165 evaluable Implants, within 9 months since insertion, we can declare that there is no evidence for the initial Implant clogging rate exceeding 10%. This acceptance criterion will be adjusted based on the actual number of evaluable Implants at end of study. The proportion of Implants

## Appendix 21

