#### 7.3 THE LEVEL OF SIGNIFICANCE AND THE POWER OF THE DEVICE CLINICAL INVESTIGATION

The significance level used for Implant clogging data analysis is 0.05 and a one-sided test will be performed. 80% statistical power was used in above sample size section.

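### Clogging assessment is triggered by explantation, but the acceptance rule counts all Implants and leaves the status of an unexplanted Implant undefined

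*Protocol*

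**What the plan says.** **Trigger.** Protocol 5.1.1.5 opens with "If an Implant is explanted, it will be analyzed for possible clogging using the following assessments". CIP 5.3 says "The Implant will be assessed for possible clogging if the Implant is explanted", and CIP Table 6 repeats the condition. The assessment starts from serum ranibizumab (PK) criteria. CIP 5.3 then adds "The Implants meeting PK criteria for possible clogging will then undergo further diagnostics if explanted to confirm whether treatment failure was due to clogging".

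**Hypothesis and rule.** CIP 5.2 states "The hypothesis to be established is that the initial Implant clogging rate does not exceed 10% of Implant arm patients at Month 9". CIP 7.1 pools everyone who receives an Implant and sets the pass condition: "If there are 22 or fewer clogged Implants, among 165 evaluable Implants, within 9 months since insertion". It continues: "This acceptance criterion will be adjusted based on the actual number of evaluable Implants at end of study". CIP 7.3 adds "The significance level used for Implant clogging data analysis is 0.05 and a one-sided test will be performed".

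**Status of each Implant.** CIP 6.1.3 allows two outcomes only, clogged or not clogged. CIP 7.10 says that missing clogging data are not imputed. Neither section mentions Implants that were never explanted.

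**SAP.** Section 1 says the SAP replaces the protocol's analysis plan. Section 2.2.2 lists clogging as a secondary outcome, and Section 4.4.2 promises descriptive summaries of secondary endpoints. The SAP gives no clogging definition, denominator or explant rule. Section 4.1.3 defines a PK-evaluable population but does not link it to clogging.

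**The concern.** The condition for being assessed and the denominator do not match. Read literally, a clogged Implant that stays in the eye cannot be found to be clogged, and with only two outcomes it may be counted as not clogged. The reported rate is then biased downward and cannot exceed the number explanted divided by 165.

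Few explants before study end are plausible. Table 6 of the CIP expects a clogged Implant to show as worsening disease, but the lack-of-efficacy pathway in Protocol 5.1.1.3 and Table 8 consists of rescue and refill and does not list explantation. Patients who enter the extension study keep their Implants (Protocol 4.6.10.5).

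Clogging is a secondary objective and the device's functional pass/fail test. CIP 7.5 says that design changes will be mandated if the device objectives are not met, and CIP 1 says that the plan supports CE certification.

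**Working it through.** **1. Reproduce the plan's rule.**
- Implants: 3 × 60 = 180 (Protocol 6.1). Dropout for the clogging analysis: 8% (CIP 7.4). 180 × 0.92 = 165.6, so 165 is all Implants less dropout.
- Cut-off, one-sided 0.05 against 10%, normal approximation: 165 × 0.10 + 1.645 × √(165 × 0.10 × 0.90) = 22.84. The rule fails at 23 or more and passes at 22 or fewer, as stated.
- Exact check: P(X ≥ 23) = 0.0647 and P(X ≥ 24) = 0.0399, so an exact 0.05 rule would allow one more. The highest passing observed rate is 22/165 = 13.3%.
- CIP 7.3 says "80% statistical power was used in above sample size section" but gives no alternative rate. With all 165 assessed, 80% power corresponds to a true rate of about 16.1%.

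**2. Literal reading: only explanted Implants can count as clogged, denominator 165.** Let m be the number explanted and p the true clogging rate, with explantation unrelated to clogging. The counted number is X ~ Binomial(m, p), and P(pass) = P(X ≤ 22). Since X cannot exceed m, P(pass) = 1 for every p when m ≤ 22. The documents do not give m, so the values below are assumptions. For scale only, 8% of 180 is about 14.

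| Explanted, of 165 | p = 15% | p = 20% | p = 30% | p = 50% |
|---|---|---|---|---|
| 22 or fewer | 100% | 100% | 100% | 100% |
| 33 (20%) | >99.9% | >99.9% | >99.9% | 98% |
| 50 (30%) | >99.9% | >99.9% | 98.8% | 24% |
| 82 (50%) | 99.8% | 95% | 31% | <0.1% |
| 110 (67%) | 94% | 56% | 1.2% | <0.1% |
| 165 (all) | 32% | 1.7% | <0.1% | <0.1% |

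**3. Clogged Implants explanted preferentially.** Let s be the share of clogged Implants that are explanted. Then P(pass) = P(Binomial(165, s × p) ≤ 22). With s = 50%, this is 93.5% at p = 20% (s × p = 10%) and 32% at p = 30% (s × p = 15%).

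**4. Alternative reading: *evaluable* means explanted, with the cut-off adjusted.** Using an exact one-sided 0.05 rule on m Implants:
- m = 16 passes at 4 or fewer; P(pass) is 80% at p = 20% and 45% at p = 30%.
- m = 30 passes at 6 or fewer; 61% and 16%.
- m = 50 passes at 9 or fewer; 44% and 4%.

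The downward bias goes, but the test is weak when few are explanted.

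**5. Alternative reading: every patient is screened by serum PK.** The screen yields only *possible* clogging. CIP 5.2 calls an Implant failed when the release element is determined to be clogged, and confirmatory diagnostics depend on explantation. No section says whether a screen-positive Implant still in the eye counts as clogged, counts as not clogged, or is excluded.

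**The case against.** The strongest reply is that the text never limits screening to explanted Implants. The PK criteria are framed per patient and run to the last visit when no refill occurs. The words *if explanted* in the CIP 5.3 sentence on further diagnostics would be redundant had only explanted Implants been screened. Serum is drawn monthly in all Implant patients (Protocol Appendix 1), and ophthalmoscopy looks for visible clogging each month (Protocol 4.6.4 and 5.1). The cut-off moves with the evaluable number and missing data are not imputed, so unassessed Implants may leave the denominator. The nine-month limit applies to clogging, not to the explant date: completers are explanted unless they enter the extension (Protocol 4.6.10.5), and all are explanted if results do not warrant further work (Protocol 4.4.2). The SAP also confines statistical tests to the primary endpoint (Section 4.4), so the pass/fail rule may no longer be operative.

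Most of this stands. It shows that the literal reading is not the only one and that later explants could supply confirmation. It does not settle the matter. *Evaluable* remains undefined, ophthalmoscopy is not among the clogging criteria in Protocol 5.1.1.5 or CIP 5.3, explantation of everyone is contingent on the results, and a screen-positive Implant left in place has no status. The SAP's silence leaves all of this open.

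**Conclusion.** The concern holds in conditional form. Explantation is the stated trigger, the planned denominator is all Implants less dropout, and the status of an unexplanted Implant is undefined. If only explanted Implants can count as clogged and 165 is kept, a pass is certain at 22 or fewer explants and remains very likely at a true 30% rate up to about 50. At a true 20% rate, P(pass) ranges from 1.7% with all assessed to above 99.9% with 50 or fewer explanted, so ascertainment can decide the result. These figures rest on assumed explant numbers and, in the table, on explantation unrelated to clogging.

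A reader might infer that the test passes almost whatever the true rate, or that the reported rate is capped at a few percent. The documents do not support that as a general statement. It requires few explants, a number they do not give; it fails if about two thirds or more are assessed; and a serum screen of everyone is a permissible reading. Nor do they say that unexplanted Implants are counted as not clogged. That is an inference from the two-outcome endpoint and the pooled denominator.

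**What to change.** In Protocol 5.1.1.5, CIP 5.3 and 7.1, and the SAP:

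- Apply the serum PK criteria to every Implant patient through Month 9, whether or not explanted. Use one version of the criteria: Protocol 5.1.1.5 and CIP 5.3 differ for the 10-mg/mL arm before the first refill.
- Define *evaluable* as having sufficient PK data to apply the criteria, and adjust the cut-off to that number.
- Report PK-positive (possible) and explant-confirmed clogging separately, by dose, with the numbers screened and explanted.
- Show bounds with unconfirmed PK-positive and unassessed Implants counted first as clogged and then as not clogged.
- Flag PK samples taken after rescue or fellow-eye ranibizumab, which could raise serum levels and hide a clogged Implant.
- State in the SAP whether the CIP 7.1 pass/fail rule still applies.

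The cost is wording and a little more analysis work; the monthly samples are already scheduled. The downside is misclassification in both directions, since the CIP itself calls serum PK too variable to show Implant function (Table 6 and Section 5.3). For that reason PK-positive Implants should not be counted as clogged by default, and the bounds are needed.

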## **Appendix 21**

### **Ranibizumab Port Delivery System: Device Clinical Investigation Plan (cont.)**

The Implants meeting PK criteria for possible clogging will then undergo further diagnostics if explanted to confirm whether treatment failure was due to clogging. The “implant complete clogging” failure statistics will be summarized across all patients based on the first 9 months of Implant insertion.

#### **5.4 RISKS AND ANTICIPATED ADVERSE DEVICE EFFECTS THAT ARE TO BE ASSESSED**

At the end of the study, the incidence of “Prespecified RPDS-associated AEs” will be compared between subjects receiving ranibizumab from the Implant and the control subjects receiving ranibizumab as ITV injections:

- Vitreous hemorrhage associated with a > 30-letter decrease in BCVA on the ETDRS chart compared with the last assessment of BCVA prior to the onset of vitreous hemorrhage lasting >1 month
- Reduced VA (>30-letter loss from previous scheduled visit)
- Traumatic cataract
- Endophthalmitis
- Damage to sclera
- Retinal detachment
- Interference of the Implant with visual field

In addition, ocular AEs and serious adverse events (SAEs) attributed by the investigator to: 1) the Implant insertion procedure, 2) the Implant refill procedure, 3) Implant explantation procedure, and 4) the Implant and other RPDS components, will be reported.

Please also refer to the protocol Section 6.5.1.

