**Table 2 Dosing Guidelines Prior to Screening**

Historical anti-VEGF use in the study eye within the last 9 months prior to screening	Open-label ranibizumab dose(s) required prior to screening	Comments
Anti-VEGF treatment naive	2	The Sponsor will provide 2 ranibizumab doses prior to screening a
Single previous anti-VEGF dose	1	The Sponsor will provide 1 ranibizumab dose prior to screening a
2–8 prior anti-VEGF dose AND most recent dose was aflibercept or bevacizumab	1	The Sponsor will provide 1 ranibizumab dose prior to screening a
2–9 prior anti-VEGF dose AND most recent dose was ranibizumab	0	Patients can proceed directly to screening

VEGF = vascular endothelial growth factor.

a In the case of a pause of patient enrollment, additional ITV ranibizumab doses will be provided before receiving study drug, until enrollment and implant insertion surgeries recommence. Patients who exceed 9 total anti-VEGF doses before receiving the study drug will be excluded from the study.

A patient's screening visit should occur no sooner than 7 days following administration of the last ITV ranibizumab treatment in the study eye. All patients will be enrolled in the study on the day of their randomization visit and receive their Day 1 study treatment after conclusion of the Randomization visit. If necessary, the Day 1 study treatment may be scheduled at a later date.

Randomization visit cannot occur earlier than 28 days and no later than 37 days after the patient's last ITV ranibizumab treatment.

Day 1 study treatment visit cannot occur earlier than 28 days after and no later than 37 days after the patient's last ITV ranibizumab treatment, unless a patient randomized to the Implant arm needs more time to interrupt aspirin or NSAID usage 7 days before Day 1 (see Section 4.3.2.3). For these patients, Day 1 study treatment visit must occur no later than 45 days after the patient's last ITV ranibizumab treatment.

Patients who are randomized to the Implant treatment arms will have scheduled safety visit assessments on Day 2 ( $\pm 0$ ), Day 7 ( $\pm 2$  days), and Day 14 ( $\pm 2$  days) after their Day 1 visit. Starting at the Month 1 visit, the patients in the Implant treatment arms will be assessed monthly for the need for Implant refill with ranibizumab according to the

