**Table 3 Ranibizumab Dosing and Safety Assessment Schema**

Visit	Day				Month									Month X b	Final/ET visit
	1 a	2	7	14	1	2	3	4	5	6	7	8	9		
Implant insertion/refill c	x				Refill Implant if refill criteria are met										NA
Safety assessment visits d		x	x	x	7 Days after each Implant refill										NA
ITV injection e	x				x	x	x	x	X	x	x	x	x	x	NA

ET=end of treatment; ITV=intravitreal; NA=not applicable.

- a The Day 1 treatment in all treatment arms (Implant and ITV injection) will occur on such date so that no fewer than 28 days and no more than 37 days have elapsed from patient's last study eye ranibizumab ITV treatment.
- b Month X visits: After completion of the Month 9 visit, the study patients in the Implant arms will continue monthly evaluation for refill according to the Month X schedule of assessments (see Appendix 1) until the Sponsor decides, based on the primary analysis results, to either terminate the study and discontinue study treatment or offer patients entry into the RPDS Extension Study. The ITV arm patients will continue to be treated monthly according to the Month X schedule of assessments (see Appendix 2) until the Sponsor decides, based on the primary analysis results, to either terminate the study and discontinue study treatment, or offer patients entry into the RPDS Extension Study.
- c Starting at the Month 1 visit, Implant treatment arms will receive a refill with ranibizumab only if protocol refill criteria are met (see Section 3.1.1).
- d There will be safety assessment visits on Days 2, 7, and 14 after the Implant insertion and then 7 days after each Implant refill. These safety assessment visits are not applicable to the ITV injections treatment arm.
- e ITV injection arm patients will be treated monthly regardless of meeting the re-treatment criteria.

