### **6.5.1 Adverse Events**

Verbatim descriptions of treatment-emergent adverse events will be mapped to thesaurus terms. Treatment-emergent adverse events will be defined as events beginning during or after surgical insertion/explantation of the Implant or the first ranibizumab ITV injection through the completion of the study or until a patient discontinues prematurely. Adverse events will be tabulated by body system, high-level term, and preferred term. Separate summaries will be prepared for non-ocular and ocular adverse events, with events in the study eye and fellow eye summarized separately. Serious adverse events will be summarized similarly. Adverse events leading to discontinuation from the study or treatment will be listed and tabulated.

ADEs are adverse events that are considered to be related to the RPDS and to the use of the RPDS. Of particular interest are the following "Prespecified RPDS-associated adverse events":

- Vitreous hemorrhage associated with a >30-letter decrease of BCVA on ETDRS chart compared with the last assessment of BCVA prior to the onset of vitreous hemorrhage lasting > 1 month
- Reduced VA (> 30 letters loss from previous scheduled visit)
- Traumatic cataract
- Endophthalmitis
- Damage to sclera
- Retinal detachment
- Interference of the Implant with visual field

In addition to the "Prespecified RPDS-associated adverse events", any other ocular adverse events and serious adverse events attributed by the investigator to the:

1) Implant insertion procedure, 2) Implant refill procedure, 3) Implant explantation procedure, and 4) study drug, will be reported.

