### Ranibizumab Port Delivery System: Device Clinical Investigation Plan (cont.)

that clog within 9 months and its 90% confidence interval will be estimated based on the binomial distribution.

In addition, the safety data from three Implant arms will be pooled and compared with monthly ITV injection arm. The summary statistics (frequency and percentage) will be provided by Implant arm and monthly ITV arm. The safety assessment will review the following:

- AEs
- SAEs
- “Prespecified RPDS-associated AEs” (see protocol Section 6.5.1)

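### The Implant–ITV comparison of Reduced VA is partly confounded with the visit schedule, mainly for short losses soon after insertion or refill

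*Protocol*

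**What the plan says.** CIP 5.4 lists seven prespecified device-associated events whose incidence "will be compared between subjects receiving ranibizumab from the Implant and the control subjects receiving ranibizumab as ITV injections". One of them is "Reduced VA (>30-letter loss from previous scheduled visit"; Protocol 6.5.1 gives it as "Reduced VA (> 30 letters loss from previous scheduled visit", and CIP 4.2 and 14.7 repeat it. No duration or confirmation is required. The vitreous hemorrhage item in the same list is different: it takes a letter loss "compared with the last assessment of BCVA prior to the onset of vitreous hemorrhage lasting >1 month".

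CIP 7.1 says that "the safety data from three Implant arms will be pooled and compared with monthly ITV injection arm", as frequencies and percentages.

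The two schedules differ. Under Protocol 3.1, Table 3: "There will be safety assessment visits on Days 2, 7, and 14 after the Implant insertion and then 7 days after each Implant refill". The same footnote adds: "These safety assessment visits are not applicable to the ITV injections treatment arm". Protocol 3.1 also calls these visits scheduled: "Patients who are randomized to the Implant treatment arms will have scheduled safety visit assessments on Day 2". Protocol Appendix 1 marks BCVA at Days 2, 7 and 14, at every monthly visit and at safety visits. Appendix 2 (ITV) marks it at randomization/Day 1, at monthly visits and at the final visit only.

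The SAP supersedes the protocol's analysis plan (SAP 1 and 2.1). It keeps the prespecified device-associated events as a safety outcome (SAP 2.2.3) but does not define them. Its named list of Implant-related events (SAP 4.6) does not include Reduced VA.

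**The concern.** An event defined against the previous scheduled visit depends on how visits are spaced, and here spacing differs by arm. Two distortions follow.

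- **Over-detection of short losses in the Implant arms.** A drop of more than 30 letters on Day 2 that recovers before Month 1 is found by a mandated test in an Implant patient. In an ITV patient it is found only if symptoms or clinical judgement lead to an unscheduled visit.
- **Under-counting of stepwise loss in the Implant arms, on one reading.** If a safety visit can be the previous scheduled visit, the reference resets at each one. A loss of 20 letters by Day 2 and another 15 by Day 7 contains no single step above 30. The same 35 letters by Month 1 is an event in an ITV patient.

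The comparison informs the safety judgement in CIP 7.5, where the adverse event profile must be acceptable against ITV dosing. The plan is aware of the extra visits, since CIP 6.1.2 cites them as one reason the Implant/ITV assignment cannot be masked. CIP 6.4.3, on foreseeable factors that may compromise interpretation, nevertheless says none apply. Nothing in either document restricts the comparison to visits both arms attend.

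**Working it through.** The documents give no figure for this comparison, so there is nothing of theirs to reproduce. The checks below use their visit schedules.

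**1. Scheduled comparisons.** From Appendices 1 and 2, with R = number of refills:

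- First month: 4 Implant (Days 2, 7, 14 and Month 1) against 1 ITV.
- Through Month 9: 3 + 9 + R = 12 + R Implant against 9 ITV. That is 12 against 9 at R = 0 (ratio 1.33) and 14 against 9 at R = 2 (ratio 1.56).

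**2. Extra looks alone.** Suppose each comparison has the same chance p of a spurious loss above 30 letters. The only SD given is 10 letters (Protocol 6.1). It is borrowed here, and a normal distribution then gives p = 0.135%. Incidence is 1 − (1 − p)^k:

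- k = 12: 1.61%. k = 9: 1.21%.
- Difference × 180 Implant patients ≈ 0.7 patients.

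**3. Identical episodes, onset uniform over nine months.** Monthly visits are at Days 30, 60, …, 270; Implant patients add Days 2, 7 and 14. An episode of D days is detected if a scheduled test falls inside it. ITV detects 9D of 270 onset days. The early Implant visits add onset days as follows:

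- D = 5: 2 + 5 + 5 = 12.
- D = 10: Days 0–14, so 14.
- D = 20: Days 0–10, so 10 (later onsets are already caught at Day 30).

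Each refill visit, 7 days after a monthly visit, adds 5, 7 or 7 onset days respectively.

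| D (days) | ITV | Implant, R = 0 | Ratio | Implant, R = 2 | Ratio |
|---|---|---|---|---|---|
| 5 | 45/270 | 57/270 | 1.27 | 67/270 | 1.49 |
| 10 | 90/270 | 104/270 | 1.16 | 118/270 | 1.31 |
| 20 | 180/270 | 190/270 | 1.06 | 204/270 | 1.13 |

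Restricted to onsets in the first 30 days, the same model gives 17/30, 24/30 and 30/30 against 5/30, 10/30 and 20/30. The ratios are then 3.4, 2.4 and 1.5.

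**4. Identical vision courses scored by the stated rule.** Simulation of 200,000 patients, of whom 10% have the course shown. Test noise of SD 3 letters is assumed, there are no refills, and safety visits are allowed as the reference.

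| Course | Implant | ITV |
|---|---|---|
| 40-letter drop at Day 1, lasting 7 or 20 days | 9.8–10.0% | 0.0% |
| Same drop lasting 60 days | 9.8% | 9.8% |
| Permanent 40-letter drop at a random time | 9.9% | 9.9% |
| Gradual 40-letter loss over 30 days | 0.4% | 9.9% |

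The last row can be checked by hand. By Day 14 the loss is 40 × 13/30 = 17.3 letters, so the largest Implant step, Day 14 to Month 1, is 40 − 17.3 = 22.7 letters. The single ITV step is 40. If the reference were the previous monthly visit, this row would be equal in the two arms.

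**The case against.** A reader might infer that the whole Implant–ITV difference in Reduced VA is produced by the schedule. The documents do not support that, for several reasons.

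- The word scheduled fixes the reference visit, not where the loss must be found. A loss seen at an unscheduled visit can qualify. Those visits include BCVA and are open to any randomized patient (Appendix 5), and every patient is called about 3 days after each treatment (Protocol 5.1). It would therefore be wrong to say that short losses in ITV patients go unmeasured. This stands, but only as a partial offset, because a call and a judgement are not the same as a mandated test.
- The resetting reference depends on safety visits counting as scheduled. Protocol 3.1 uses the word for both monthly and safety visits, so the point is conditional.
- The ratios of 1.5 to 3.4 apply only to the first 30 days, while CIP 5.4 compares incidence at the end of the study.
- Protocol 6.5.1 presents the list among adverse device effects, which investigators report and attribute. Not every measured drop becomes an event.
- The comparison is descriptive, and CIP 7.5 sets no threshold on Reduced VA.
- Early loss after surgery is a real effect of the procedure. Removing it from the randomized comparison would hide harm.

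All of these stand and limit the size of the point.

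Two further inferences fail. The overlap between Reduced VA and the hemorrhage item is not a contradiction: one captures persistent hemorrhage-related loss, the other any large loss. Nor does gradual loss go unseen, because SAP 4.4.2.1 gives letter-loss proportions from baseline by arm and an uncensored summary of change from baseline. Neither summary, however, reports the more-than-30-letter event on a common footing.

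**Conclusion.** The Implant–ITV comparison of Reduced VA is partly confounded with the visit schedule. Transient losses that recover before the next monthly visit are over-detected in the Implant arms. Stepwise or gradual losses are under-counted there if safety visits count as the reference. Sudden losses still present at the next monthly visit are counted equally.

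Over nine months with no refills the detection ratio is about 1.06 to 1.27 for episodes of 20 down to 5 days, rising to about 1.13 to 1.49 with two refills. Only for short losses soon after insertion or refill can the schedule create most of the contrast.

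These ratios assume the same underlying episodes in both arms, uniform onset, and no ITV detection through unscheduled visits. They measure the opportunity to detect, not reported events. The documents give no rate of transient loss above 30 letters. The Phase I figure of 15% for insertion-related VA decrease (Protocol 1.3) has no letter threshold and comes from 20 patients, so it cannot be turned into an expected count. The consequence is a descriptive safety contrast that is hard to interpret, not a wrong test.

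**What to change.** Add to the existing analysis; do not replace it.

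1. Keep the all-visit tabulation of Reduced VA, so that early post-operative loss stays visible.
2. Add to the SAP and CIP 5.4 an Implant–ITV comparison of loss above 30 letters at the monthly visits both arms attend. Use randomization BCVA as the common reference, with the previous monthly visit as a second version. The second version picks up a patient who gains letters and then loses more than 30. Through Month 9 each arm then has 9 comparisons.
3. Report losses found only at Implant-only visits (Days 2, 7 and 14, post-refill, post-explantation) on a separate line, with duration.
4. Define the event in the SAP, and state there and in Protocol 6.5.1 and CIP 4.2, 5.4 and 14.7 which visit is the reference and whether safety visits qualify.

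The cost is wording and one extra table; all the BCVA data are already collected, and no visit or treatment rule changes. The downside is that the common-visit comparison does not capture transient post-surgical loss, so it must be read beside the all-visit table.
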